5.5 Key inclusion criteria

Participants must be age 55-75, own a smartphone, be enrolled in GeneMatch, know their genetic testing results (APOE4), and able to provide informed consent

5.6 Key exclusion criteria

1) Inability to provide informed consent; 2) does not have daily access to a smartphone compatible with the wearable device and not willing to use a device that we can provide them; 3) already enrolled in another physical activity study; 4) unable to ambulate independently; 5) any other medical conditions that would prohibit participation in physical activity program;

6. Subject recruitment

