appealing approach to increase engagement in healthy behaviors because it makes the “hard stuff” fun by turning obligations into goals and challenges.¹⁰ Second, mobile technologies which are increasingly used by older adults¹¹ can be used to accurately,¹² and unobtrusively help set and maintain specific daily and weekly activity goals. Third, social incentives can be used to enhance these effects and reinforce habit formation to prevent regression. Social incentives are powerful influences that motivate individuals to change their behaviors based on social ties or connections.¹⁴⁻¹⁷ For example, an individual’s mobility is higher when a family member or friend has increased mobility.¹⁷ On closer inspection, such interactions contain many powerful levers to change human behavior including peer support, accountability, and collaboration. Since social networks are ubiquitous, approaches that harness social incentives could be scaled more broadly at lower cost than interventions relying on health care professionals to motivate and monitor physical activity in older adults at risk for ADRD. Our group has successfully used gamification, mobile technologies, and social incentives to increase activity in several non-ADRD populations.

One challenge to studying behavioral interventions to improve physical activity in the ADRD population has been enrollment with most studies to date enrolling from clinics which limits sampling; prior studies have also used variable definitions of “elevated risk” for dementia. In this study, we identify and recruit participants utilizing a novel, national cohort of individuals with quantifiable risk using genetic testing from the GeneMatch study.^{18,19}

5. Study design

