5.4 Accrual

We will aim to enroll and randomize 100 participants. We estimate a standard deviation of 2500 steps and a sample of 100 participants allocated in a 1:1 distribution (50 in each arm), will ensure at least 80% power to detect a 1000 step difference. This calculation assumes a 10% dropout rate and a conservative Bonferroni adjustment of the type I error rate with a 2-sided alpha of 0.017.

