6.1 General

Participants will be recruited from the Alzheimer Prevention Initiative's (API) GeneMatch registry, which is managed by the Banner Alzheimer's Institute. GeneMatch maintains a registry of older adults who live in the United States and do not have a diagnosis of cognitive impairment. GeneMatch will identify potential participants based on age (55-75). GeneMatch will invite these individuals through an email invitation and a study description on their GeneMatch dashboard. Potential participants will have the option to accept or decline the study invitation. If participants accept, they acknowledge that their information will be shared with the study team and that a member of the study team will contact them. Those who decline the invitation will not be contacted again, and none of their information will be shared with the study team. Study coordinators will contact potential participants who accept the invitation via phone/email to further assess interest and answer questions related to the study.

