Pre-commitment: Each participant signs a contract agreeing to try their best to achieve their daily step goal. Pre-commitment helps to motivate behavior change by increasing perceived accountability.^{18,19} Points: Each week, participants are endowed 70 points (10/day) prospectively rather than awarded after goal achievement to leverage the BE concept loss aversion that individuals are more motivated by immediate losses than gains.²⁰⁻²² Each day that the goal is not met, they are informed that they lost 10 points. Points are replenished at the start of the week to leverage the BE concept of the “fresh start effect” that individuals are more motivated for aspirational behavior around temporal landmarks such as the start of the week.⁵⁰ Levels: At the end of the week, if the participant has 40 points or more, he or she will advance one level. The levels include: blue (lowest), bronze, silver, gold, platinum (highest). If they have < 40 points, they drop down one level. This creates a sense of achievable goals (goal gradients)²³ and anticipated regret.²⁴⁻²⁷ Each participant begins in the middle (silver), so higher levels seem within reach and they will feel a sense of loss from dropping down a level. Support partner: Each participant will select a spouse, family member, or friend that they see often to serve as a sponsor and receive a weekly email participant’s progress including points, game level, and average step count. This supportive sponsor will help to enhance social incentives to motivate the individual towards his or her goal.¹³

Follow-Up Period. At the end of the 12 week Intervention Period participants will enter a 6 week Follow-Up Period during which interventions will cease but passive data collection of step counts will continue.

Exit Survey. Participants will complete an end-of-study questionnaire on their experience with the wearable device and intervention design. Participants will be asked to describe elements that helped them to achieve their physical activity goals (and elements that did not help) and suggestions on how to improve the design of the interventions.

Upon completion of the study, participants will receive payment of \$100 on a pre-paid debit card (Clincard).

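### Household members can both be randomised, and a control participant can be named as a game player's support partner, so some controls could be exposed to the game

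*Combined protocol and SAP*

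**What the plan says.** Section 5.6 lists five exclusions. The nearest to a bar is for people "already enrolled in another physical activity study", which concerns a different study. The inclusion criteria in 5.5 cover age, smartphone, registry membership, known APOE4 result and capacity to consent, with no household condition. Under 6.1 the registry selects on age, and "GeneMatch will invite these individuals through an email invitation and a study description on their GeneMatch dashboard". The screening survey in 8.3 asks about other research and whether a study partner is available. It does not ask whether someone close to the person is in this trial.

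Under 8.2, individuals are randomised 1:1, stratified only on baseline steps. Controls get the device and nothing more through follow-up. In the game arm, "Each participant will select a spouse, family member, or friend that they see often to serve as a sponsor", and that person is emailed weekly with the player's steps, points and level. Nothing says the person chosen must be outside the trial.

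Section 4 gives the rationale for the social component: an individual's "mobility is higher when a family member or friend has increased mobility".

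**The concern.** In most individually randomised trials, a couple split between arms is a minor matter. Here the intervention works through close relationships, so a control who lives with a game participant, or is named as the partner, sits on the pathway that the trial is testing. A control named as partner would also receive something that 8.2 says controls do not receive.

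The route runs from the game to the control. If it operates, control steps rise and the estimated difference shrinks. The analysis plan in section 9 has no step that would identify linked participants or show how far they affect the result.

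**Working it through.** **Inputs from the documents (section 5.4).** The plan says "We estimate a standard deviation of 2500 steps"; "a sample of 100 participants allocated in a 1:1 distribution (50 in each arm"); 10% dropout, so 45 per arm evaluable; a difference of 1000 steps; and "a conservative Bonferroni adjustment of the type I error rate with a 2-sided alpha of 0.017" (0.05/3 = 0.0167).

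**Inputs assumed, because the documents give none.** Linked pairs k = 2, 5 or 10 among the 100 randomised. Share of the effect passed to an exposed control g = 0.5 or 1. Every control in a split pair counts as exposed.

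**Step 1: the plan's own figure.** The plan says the sample "will ensure at least 80% power to detect a 1000 step difference". With the stated inputs and a normal approximation:

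- 45 per arm: SE = 2500 × √(2/45) = 527; 1000/527 − 2.387 = −0.490; power = 31.2%.
- 50 per arm: SE = 2500 × √(2/50) = 500; 2.000 − 2.387 = −0.387; power = 34.9%.

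The 80% is not reproduced. At 45 per arm it would need an SD near 1470. That is a separate matter from this point. I therefore show power both for the stated SD and for a design that truly has 80%.

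**Step 2: exposed controls.** With 50 of 100 in each arm, a given pair is split with probability 50/99 = 0.505. Stratification changes this little. Expected split pairs are k × 0.505 = 1.0, 2.5 and 5.1. Divided by 50 controls, the exposed share is c ≈ 2%, 5% and 10%.

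**Step 3: dilution.** Difference observed = 1000 × (1 − c × g).

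| Pairs | c | g | Steps lost | Difference | Power, true 80% design | Power, stated SD, 45 per arm |
|---|---|---|---|---|---|---|
| 0 | 0 | – | 0 | 1000 | 80.0% | 31.2% |
| 2 | 2% | 0.5 | 10 | 990 | 79.1% | 30.6% |
| 5 | 5% | 0.5 | 25 | 975 | 77.7% | 29.6% |
| 10 | 10% | 0.5 | 50 | 950 | 75.2% | 28.0% |
| 2 | 2% | 1 | 20 | 980 | 78.1% | 29.9% |
| 5 | 5% | 1 | 50 | 950 | 75.2% | 28.0% |
| 10 | 10% | 1 | 100 | 900 | 69.8% | 24.9% |

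**Step 4: scale.** Against a standard error of 500 to 527, a loss of 10 to 50 steps is about 2% to 10% of one standard error. At full transfer, 20 to 100 steps is about 4% to 20%.

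**The case against.** The strongest reply is that linked pairs will be rare. Both members must be in a registry that covers the whole United States, be aged 55 to 75, own a smartphone, know their APOE4 result, accept the invitation and average under 7500 steps in run-in. No passage says that couples are expected, and ten pairs would put 20 of the 100 participants in linked pairs. A control acting as partner receives emails about someone else and has no points, levels, contract or sponsor of their own, so even half transfer may be generous. The list in 5.6 is headed as key criteria, so an unwritten rule may exist. All of this limits the size of the problem, and I accept it. It does not close the gap, because nothing written prevents the exposure.

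Three stronger readings are tempting and are not supported:

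- A reader might infer that the arms will contaminate each other. The documents show a possibility, not an occurrence, and the route is one-way.
- A reader might infer that linked pairs invalidate an analysis with participant random effects only. Under individual 1:1 randomisation a pair falls in the same arm with probability 49/99, where positive correlation inflates the variance of the difference. It is split with probability 50/99, where the correlation reduces that variance. The net expectation is 49/99 − 50/99 = −1/99 of the covariance term, which is negligible.
- A reader might count two game participants who partner each other as contamination. Both were assigned to the game, and no control is exposed.

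**Conclusion.** The gap holds: the protocol permits co-enrolment within a household and permits a control to serve as support partner, and the second conflicts with the control condition in 8.2. The direction of any effect is toward no difference. The size rests on assumed pair counts and transfer: about 10 to 50 steps lost from 1000 with 2 to 10 pairs at half transfer, or about 20 to 100 at full transfer. That few pairs would arise is a judgement, since the documents give no count. This is a cheap improvement to the design. It is not evidence that the primary result would be materially biased.

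**What to change.** In 5.6, allow one participant per household: exclude anyone whose household member has consented to this study, is in its run-in, or has been randomised. The wording should not rest on being enrolled, because 5.1 counts a person as enrolled only once run-in is complete and they are randomised. A couple going through run-in together would pass such a rule. Check it with one added screening question and the shipping address already collected under 8.2.

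In 8.2, state that a support partner may not be a participant in this trial, and check this when the game participant names the partner. Controls need not name anyone.

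The planned sample size and the analysis model stay as they are. The cost is one exclusion line, one screening item and one sentence on partners. The second member of a few interested couples is turned away, and a few game participants must name a different partner.

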6.1 General

Participants will be recruited from the Alzheimer Prevention Initiative's (API) GeneMatch registry, which is managed by the Banner Alzheimer's Institute. GeneMatch maintains a registry of older adults who live in the United States and do not have a diagnosis of cognitive impairment. GeneMatch will identify potential participants based on age (55-75). GeneMatch will invite these individuals through an email invitation and a study description on their GeneMatch dashboard. Potential participants will have the option to accept or decline the study invitation. If participants accept, they acknowledge that their information will be shared with the study team and that a member of the study team will contact them. Those who decline the invitation will not be contacted again, and none of their information will be shared with the study team. Study coordinators will contact potential participants who accept the invitation via phone/email to further assess interest and answer questions related to the study.

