11.8 Resources necessary for human subjects protections

1. Abstract

Increased physical activity by walking further or more vigorously may prevent or delay the development of Alzheimer's Disease and Related Dementias (ADRD) but reaching higher levels of activity and maintaining it as a long-term habit is difficult to do. This project will use concepts from behavioral science to create a game older adults can play in order to increase their levels of activity while having fun doing it. The game is played with a support partner who is a spouse, family member, or close friend who provides feedback and encouragement to help the game-player reach activity goals and maintain them as habits over time. Participants in the game will use their own smartphone and a wristwatch that tracks activity (such as a FitBit, provided by this study) to set goals, get feedback, and play the game for 12 weeks. Participants will be asked to continue wearing the wristwatch for another 6 weeks to track activity after the game is over. To determine the effectiveness of this game, we will randomly assign 50 people to the game and 50 people to only get the wristwatch but no game component. All participants in this study will be recruited from an online registry of adults age 55-75 who have not been diagnosed with Alzheimer's (GeneMatch) which offers genetic testing on risk for ADRD to all participants. We

will recruit participants to our study who have elevated genetic risk as well as those without specific genetic risks to see if either group responds differently to the game.

2. Overall objectives

The primary objective is to assess the effectiveness of a social incentive-based gamification intervention to increase physical activity over 12 weeks with follow up of 6 weeks after the intervention concludes. We will explore whether participants who know they are higher risk (carriers of the APOE4 gene) are more responsive to the intervention than those who know they are at average risk (non-carriers of APOE4). We will also explore the feasibility of collecting measures of cognition and function remotely using standardized instruments by telephone or video calls.

3. Aims

3.1 Primary outcome: change in mean daily step count from the baseline period to the end of the 12-week intervention period.

3.2 Secondary outcome: mean daily step count during the 6-week follow up period after the end of the intervention.

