Randomization. After establishing baseline, participants will be randomly assigned to control or interventions using a 1:1 allocation and stratifying on baseline step count (< 4000, 4000-7000 steps, >7000 steps) using an electronic number generator through the WTH platform. All participants will be asked to use the wearable device during the day and at night to measure activity. Each participant will select whether he or she would like to primarily receive study communications by text message, e-mail, or automated interactive voice response phone call.

Cognition and Function Measures. Within 2 weeks of randomization (study weeks 2-4) and within 2 weeks after completing the intervention period (study weeks 15-16), participants will complete online survey-based assessments and virtual (video call) assessments of function (Timed Up and Go and 30-second Chair Stand) and cognition (Verbal Naming; Category Fluency; Trail Making; Number Span; Blind MOCA). The online surveys will be completed through the Way to Health online platform. Research staff will contact participants to schedule and conduct video calls to complete the tests of function and cognition.

Intervention Period.

Control: Participants in the control arm will receive a study device (e.g. FitBit) but no other interventions during the intervention or follow-up periods.

Intervention: Intervention participants will enter a game designed with behavioral economics (BE) concepts to address predictable barriers to behavior change during the 12-week intervention period. The components of the gamification intervention are described below:

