8.3 Instruments

Step Count: Daily step count data will be uploaded daily from participants' activity trackers.

Screening Survey: A screening survey will be administered through the study website prior to enrollment to assess eligibility for the study. The survey will query age, use of smart phone, current activity level, participation in other research, ability to safely increase physical activity, availability of study partner, and knowledge of APOE genotype.

Baseline/demographics: After consent and confirmation of eligibility, participants will complete a survey through the way to health platform to provide demographic information (Age, gender, race, ethnicity, income, education, self-report comorbidities/health conditions) as well as a shipping address for the Fitbit to be sent to.

Cognition and Function: During the first two weeks of the intervention period and the first two weeks of the follow up period, participants will complete virtual (video call) assessments of function (Timed Up and Go and 30-second Chair Stand) and cognition (Verbal Naming; Category Fluency; Trail Making; Number Span; Blind MOCA). Research staff will contact participants to schedule and conduct video calls to complete the tests of function and cognition.

Exit survey: Participants will complete an end-of-study questionnaire on their experience with the wearable device and intervention design. Participants will be asked to describe elements that helped them to achieve their physical activity goals (and elements that did not help) and suggestions on how to improve the design of the interventions.

9. Analysis plan

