Similar to our prior work,^{22,44,54} the primary analysis will fit mixed effect regression models to evaluate changes in physical activity (steps per day and minutes of MVPA) adjusting for each participant's baseline measure, time using calendar month fixed effects, participant random effects, and accounting for repeated measures. Secondary analyses will fit a fully adjusted model including other variables of interest such as participant demographic characteristics and comorbidities. We will also conduct a-priori exploratory subgroup analyses for participants with elevated risk (APOE4 carriers) and higher levels of social support on 1o and 2o outcomes. For these outcomes, we estimate a standard deviation of 2500 steps and a sample of 100 participants allocated in a 1:1 distribution (50 in each arm), will ensure at least 80% power to detect a 1000 step difference. This calculation assumes a 10% dropout rate and a conservative Bonferroni adjustment of the type I error rate with a 2-sided alpha of 0.017.

In exploratory analyses, we will compare results from virtual functional and cognitive tests at the beginning of the study (after randomization) with results during the follow up period (after intervention ends). We do not anticipate major changes in these measures and are not powered to detect minor changes – these are feasibility measures to demonstrate we can conduct virtual performance tests at multiple intervals only.

We will also conduct exploratory subgroup analyses of factors that may influence our primary outcome (change in mean steps/day) such as participant-reported social support and neighborhood walkability as determined by address/zipcode. These are factors that have been associated with steps in our prior work but this pilot will not adequately powered to detect statistical significance (we will explore for trends only).

10. Investigators

[name], MHS, MA is the Principal Investigator (PI). He is the Director of Penn Center for Evidence-based Practice; his research focuses on outcomes of hospitalization for older, vulnerable adults during transitions of care and mobile technologies to engage this population.

[name] is Co-Director of the Penn Memory Center and Director of the Penn Program on Precision Medicine for the Brain (P3MB). His research focuses on quality of life and ethical issues of disclosure of gene and biomarkers of Alzheimer's disease risk in older adults.

11. Human research protection

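### The exploratory APOE4 carrier comparison has no carrier target in recruitment and no place in the stratification; fixing both is a cheap gain in precision, though the comparison stays imprecise either way

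*Combined protocol and SAP*

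**What the plan says.** The Abstract states that the study "will recruit participants to our study who have elevated genetic risk as well as those without specific genetic risks", in order to see whether the groups respond differently. Section 2 (Overall objectives) repeats it: "We will explore whether participants who know they are higher risk (carriers of the APOE4 gene) are more responsive to the intervention" than people who know they are at average risk. Section 9 (Analysis plan) adds: "We will also conduct a-priori exploratory subgroup analyses for participants with elevated risk (APOE4 carriers) and higher levels of social support", on the primary and secondary outcomes.

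The operational sections are as follows.

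- **Invitation (6.1):** "GeneMatch will identify potential participants based on age (55-75"). Genotype is not mentioned as a selection criterion.
- **Eligibility (5.3, 5.5):** participants must "know their genetic testing results (APOE4"). Either result qualifies.
- **Screening survey (8.3):** asks about "knowledge of APOE genotype". It does not say that the result itself is recorded.
- **Randomisation (8.2):** 1:1, "stratifying on baseline step count (< 4000, 4000-7000 steps, >7000 steps"). APOE4 is not a factor.
- **Run-in (8.2):** participants averaging 7500 steps or more on days 8 to 14 are not randomised.

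No section gives a target, cap or expected share of carriers.

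**The concern.** The Abstract promises both risk groups, and the Background presents the genotyped registry as a reason for the design. Nothing in recruitment or allocation delivers a usable number in each group. As written, the carrier share is whatever the volunteers happen to be, and the split of carriers between arms is left to chance.

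The precision of a subgroup contrast is governed mainly by the smaller group. If carriers turn out to be a minority, an already wide interval gets wider, and neither the mix nor the allocation can be repaired after enrolment. At stake is how informative one exploratory comparison will be. The primary comparison between arms does not depend on it.

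**Working it through.** **The plan's own figure.** There is none for the carrier comparison. The stated power of at least 80% for 1000 steps (5.4, repeated in 9) concerns the comparison of the two whole arms. From the stated inputs, with 45 evaluable per arm, SE = 2500 × √(2/45) = 527. The critical value at two-sided 0.017 is 2.387, so power = Φ(1000/527 − 2.387) = 31%. That shortfall is a separate matter and nothing below rests on it.

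**Inputs.** From 5.4: "We estimate a standard deviation of 2500 steps", 50 per arm and 10% dropout, so 45 per arm evaluable. Assumptions of mine: carrier share p of 50%, 25% or 15%, because the documents give none; equal dropout by genotype; and two-sided 0.05 for the interaction, because no alpha is given for it.

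**Step 1: effect of the carrier share.** Per arm, carriers nc = 45p and non-carriers nn = 45(1 − p), evenly split between arms.

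- SE of the arm effect in carriers = 2500 × √(2/nc)
- SE of the carrier-by-arm contrast = 2500 × √(2/nc + 2/nn)
- 95% half-width = 1.96 × SE
- Power for a 1000-step interaction = Φ(1000/SE − 1.96)

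| Carrier share | nc, nn per arm | SE, carrier effect | SE, contrast | 95% half-width, contrast | Power for 1000 |
|---|---|---|---|---|---|
| 50% | 22.5, 22.5 | 745 | 1054 | 2066 | 16% |
| 25% | 11.25, 33.75 | 1054 | 1217 | 2386 | 13% |
| 15% | 6.75, 38.25 | 1361 | 1476 | 2893 | 10% |

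Relative to 50/50, the contrast SE is 1217/1054 = 1.15 times as large at 25% and 1476/1054 = 1.40 times at 15%. Squaring these ratios, matching the 50/50 precision would take about 33% more participants at 25% carriers and about 96% more at 15%.

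The ratios do not depend on the SD. If baseline adjustment lowered the SD to about 1470 (roughly what 80% overall power needs with 45 per arm), the 50/50 contrast SE would be 1054 × 1470/2500 = 620 and power Φ(1000/620 − 1.96) = about 36%.

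**Step 2: effect of the chance split between arms.** Take 100 randomised, 50 per arm, no dropout, and a hypergeometric split of the carriers (two-sided tails). SE = 2500 × √(sum of the reciprocals of the four cell counts).

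| Carriers | Split | Chance of this or worse | SE at this split | SE at even split | Increase |
|---|---|---|---|---|---|
| 25 | 17:8 | 6.3% | 1219 | 1155 | 6% |
| 25 | 16:9 | 16.5% | 1192 | 1155 | 3% |
| 15 | 11:4 | 9.1% | 1558 | 1400 | 11% |

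For the first row, for example, the cells are 8, 17, 42 and 33. The number of carriers matters more than how chance divides them.

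**Step 3: strata if carrier status is added.** Three step levels by two genotypes give six cells. The 7500-step exclusion leaves the top step stratum covering only averages above 7000 and below 7500, so its two cells would be nearly empty. Merged with the middle stratum, the design has 2 × 2 = 4 cells.

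**The case against.** The strongest reply is that the comparison is labelled exploratory, that Section 9 calls the study a pilot, and that even a perfect 50/50 stratified design would not settle the question. All of this stands. It limits the weight of the point but does not remove it: an exploratory estimate also needs enough people in both groups, and the better design uses the same 100 participants.

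Four further limits also stand.

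- **The shortfall is conditional.** The documents give no carrier share. If volunteers are already near 50/50, a target changes nothing.
- **Stratification is the smaller part.** Even the adverse splits above cost 3 to 11% in SE.
- **Recorded genotype is not established.** A reader might infer from the inclusion criterion that the study holds each genotype before randomisation. The documents show only that participants must know their result and are asked about that knowledge. The baseline survey does not list genotype, and 6.1 does not say which registry information is shared. Whether the registry can filter invitations on known results is also not stated.
- **A hard quota has its own risk.** Closing enrolment to the group that fills first could endanger the total of 100 within the planned year or so, and with it the primary analysis.

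**Conclusion.** The gap is in the text: an objective in the Abstract, Section 2 and Section 9 has no counterpart in 6.1 or in the randomisation paragraph of 8.2. Its cost is a contrast SE that is 15% larger at 25% carriers and 40% larger at 15%, and no larger at 50%. The carrier share is an assumption throughout. The absolute SEs also rest on the SD of 2500 and 10% dropout.

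This is a cheap improvement, not a flaw that threatens the trial. Two stronger readings are tempting and should be resisted. One is that the trial as written cannot answer a question that the balanced design would answer. It would not: at 50/50 the half-width is still about 2070 steps and power for a 1000-step interaction about 16%. The other is that carriers will be scarce, at about 7 to 11 evaluable per arm. That is only the 15 to 25% end of an assumed range, and no figure in the documents supports it over 50%.

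**What to change.** 1. **8.3, screening survey:** record the APOE4 result itself (carrier yes or no), before randomisation. The Section 9 subgroup analysis needs this in any case.
2. **6.1:** issue invitations by age and APOE4 status among registrants who know their result, aiming for about 50 carriers and 50 non-carriers. Make it a soft target, relaxed if the rarer group lags, so that the total of 100 is protected. Confirm with the registry that it can select invitees this way.
3. **8.2, Randomization:** add carrier status as a stratification factor, as a secondary benefit, and merge the step stratum above 7000 with the one below it.
4. **Section 9:** state that the carrier comparison is exploratory and imprecise even at 50/50, and report the carrier-by-arm contrast as an estimate with a 95% confidence interval.

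The cost is one protocol amendment, a survey item and changes to the invitation and randomisation settings, with no added participants. The rarer group may fill more slowly, and the enrolled mix will not mirror the registry. If the sponsor prefers not to change recruitment, the protocol should at least state the expected carrier share and the precision that follows from it.
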